5.3.1 Imaging Assessment for the Study

Any incidental findings of potential clinical relevance that are not directly associated with the objectives of the protocol should be evaluated and handled by the Study Investigator as per standard medical/clinical judgment.

Imaging is an important component of the study. All subjects will undergo standardized MRI at baseline and at the Day 28 visit. Images may be evaluated locally, but must also be submitted for

analysis by the Imaging Adjudication Committee. Results of centralized analysis will not be returned to the sites.

In addition, various types of imaging may be used for the clinical evaluation of suspected efficacy or safety endpoints. For these events, investigators should perform and analyze imaging and other assessments according to their normal clinical practice and the local standard of care, and base any treatment decisions on the local interpretation. Results of these assessments will also be submitted for adjudication by the CEC. Results of the adjudication by the CEC will not be returned to the sites.

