5.3.2 Bleeding

The main safety outcome of the study is bleeding. Subjects with bleeding or suspected bleeding will undergo confirmatory laboratory or other testing (ultrasound [US], CT, MRI, etc.) and an (S)AE CRF must be completed. All clinically overt bleeding events that lead to medical treatment or evaluation, or discontinuation of study medication must be submitted for adjudication. Major and clinically relevant non-major bleeding will be adjudicated by CEC according to definitions specified in the CEC charter.

Acute clinically overt bleeding is defined as new onset, visible bleeding or signs or symptoms suggestive of bleeding with confirmatory imaging techniques which can detect the presence of blood (eg, US, CT, MRI).

The definition of major bleeding described below is adapted from the International Society on Thrombosis and Hemostasis (ISTH) definition.

Major bleeding event is defined as a bleeding event that is:

- Acute clinically overt bleeding accompanied by one or more of the following:
 - A decrease in hemoglobin (Hb) of 2 g/dL or more
 - A transfusion of 2 or more units of packed red blood cells
 - Bleeding that occurs in at least one of the following critical sites:
 - ◆ Intracranial
 - ◆ Intra-spinal
 - ◆ Intraocular (within the corpus of the eye; thus, a conjunctival bleed is not an intraocular bleed)
 - ◆ Pericardial
 - ◆ An operated joint and requires re-operation or intervention
 - ◆ Intramuscular with compartment syndrome
 - ◆ Retroperitoneal
- Bleeding that is fatal

Clinically relevant non-major bleeding event is defined as a bleeding event that is:

- Acute clinically overt bleeding

- Does not satisfy additional criteria required for the bleeding event to be defined as a major bleeding event
- Requires medical treatment or evaluation, or leads to discontinuation of study medication.

Minor bleeding event is defined as any adjudicated bleeding event that does not meet the criteria for Major Bleeding or Clinically Relevant Non-Major Bleeding.

Fatal Bleeding Event is defined as a bleeding event that the CEC determines is the primary cause of death or contributes directly to death.

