5.4.2.1 Magnetic Resonance Imaging

Magnetic resonance imaging (MRI) has now become the primary noninvasive modality for stroke imaging. Diffusion weighted imaging (DWI) is highly sensitive in identifying hyperacute and acute cerebral infarction, showing ischemia within minutes of vascular occlusion.⁸ The stroke lesion appears bright on DWI scans in the acute and subacute stages, while chronic infarcts are characterized by dark signal on DWI⁸. Fluid-attenuated inversion recovery (FLAIR) MRI has had important applications in the imaging of stroke patients⁹. FLAIR depicts areas of tissue T2 prolongation while suppressing CSF signal, offering a sensitive method to detect lesions.⁸ Hyperintensity of the ischemic brain in acute strokes is seen on FLAIR as early as 4 to 6 hours after infarction at a time when T1-weighted images (T1WI) and T2-weighted images (T2WI) are usually normal. After the first 24 hours, T1WI, T2WI, and FLAIR are most useful in subacute and chronic stroke. FLAIR and DWI sequences will be used to identify any new ischemic infarction lesions as compared to the baseline MRI. Details of study-required MRI parameters will be described in the study imaging manual.

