7.2 Independent Central Adjudication Committees

The clinical events adjudication committee (CEC) will be a blinded, independent group of clinicians experienced in the diagnosis of stroke and other cardiovascular diseases who are not otherwise involved with the study. The CEC will evaluate clinical events related to study endpoints, including adjudication of suspected symptomatic stroke, suspected myocardial infarction, bleeding, and death. The full role of the CEC and criteria for evaluation of clinical events will be defined in the CEC charter.

The imaging adjudication committee (IAC) will be an independent group of neuroradiologists experienced in the interpretation of brain MRI images. The IAC will evaluate blinded MRI images obtained no later than 24 hours after randomization and at the Day 28 study visit for detection of unrecognized brain infarctions. The full role of the IAC and criteria for evaluation of unrecognized brain infarction will be defined in the IAC charter.

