7.2.2 Relevant Protocol Deviations

Relevant deviations from the study protocol will be documented and accounted for in presenting the data summaries, listings and descriptive statistical analyses. Any changes from planned protocol-specified analyses will be defined in the SAP and reported in the CSR. The relevant protocol deviations are described in the table below.

Table 7.2.2-1: List of Relevant Protocol Deviations

Number	RPD Criteria
1	Subject randomized but not dosed
2	Error in treatment assignment (resulting in a subject receiving a treatment other than that assigned by the IVRS) during the first 28-day interval
3	Poor treatment compliance for either BMS-986141 or ASA (compliance less than 80% or more than 120%) during first 28-day interval
4	Randomized subjects with history of atrial fibrillation (AF) other than transient AF related to cardiac surgery at enrollment (per Exclusion Criteria 1a from the protocol)
5	Randomized subjects with unrecognized or misdiagnosed intracranial hemorrhage (ICH) as determined by the central reader based on the baseline study specific MRI (presence of type 1 or 2 parenchymal hematoma)
6	Randomized subjects who took no dose of ASA or dose of ASA not within limits designated by the protocol for ≥ 5 consecutive days in the first 28 days of the treatment period
7	Randomized subjects who took oral anticoagulants or prohibited antiplatelet therapy, other than study medication, for > 2 consecutive days during the first 28days of the treatment period
8	Randomized subjects that were treated with a strong CYP3A4 inhibitor for > 5 days during the first 28 days of the treatment period ^a

a: CYP3A4 inhibitors will be defined in a separate file maintained by the study team and will be classified as weak, moderate, or strong.

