All AEs will be coded and grouped into Preferred Terms (PT) by System Organ Class (SOC), using the most current available version of Medical Dictionary for Regulatory Activities (MedDRA). Summaries of AEs will use the version of MedDRA that is current at the time of database lock. All recorded adverse events will be listed and tabulated by SOC, PT, treatment and overall. Values for ECGs, vital signs, and clinical laboratory test results will be summarized by treatment. Abnormal results for ECG, vital signs and clinical laboratory tests that fall outside the pre-specified criteria will also be listed and summarized. In addition, ECG readings will be evaluated by the Investigator and abnormalities, if present, will be listed.

7.6.1 *Major Bleeding and Clinically Relevant Non-Major Bleeding*

The proportion of subjects with adjudicated bleeding events which occur on or after the first dose of study treatment and within 4 days after the last dose of study treatment will be summarized by treatment. Point estimates and 95% exact CIs for event rates of each of the below bleeding endpoints will be presented by treatment, together with point estimates and 95% exact CIs for the difference of event rates between each BMS-986141 arm and placebo. The following bleeding endpoints will be analyzed using these methods.

- The proportion of subjects with the composite of adjudicated major bleeding and CRNM bleeding
- The proportion of subjects with all reported bleeding
- The proportion of subjects with intracranial hemorrhage

All adjudicated bleeding events will be listed. In addition, the proportion of subjects with confirmed major bleeding or clinically relevant non-major bleeding events occurring during the treatment period will be summarized by treatment group for each of the following factors.

- Stroke severity (based on National Institutes of Health Stroke Scale NIHSS) at study entry
 - NIHSS Score of 0 (No stroke symptoms)
 - NIHSS Score of 1-4 (Minor stroke)
 - NIHSS Score of 5-15 (Moderate stroke)
- Lacunar infarct at study entry
 - Yes
 - No

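### No systematic hemorrhage read of the Day 28 MRI is specified, so asymptomatic intracranial bleeding is captured only if a site reads and reports it, while silent infarction is read centrally in every subject

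*Protocol*

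**What the plan says.** **Imaging.** Protocol 5.3.1: "All subjects will undergo standardized MRI at baseline and at the Day 28 visit". Blinded neuroradiologists of the imaging adjudication committee (IAC) compare the two scans for new infarction (Protocol 5.4.2, SAP 4.1.2). Protocol 7.2 describes the committee as evaluating scans from around randomization and "at the Day 28 study visit for detection of unrecognized brain infarctions". On technique, Protocol 5.4.2.1 states: "FLAIR and DWI sequences will be used to identify any new ischemic infarction lesions"; other parameters are left to the imaging manual. Under 5.3.1, local reading is optional and central results do not go back to sites.

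**Bleeding.** Protocol 5.3.2 sets the rule for referral to the clinical events committee (CEC): "All clinically overt bleeding events that lead to medical treatment or evaluation, or discontinuation of study medication must be submitted for adjudication". Overt bleeding is "new onset, visible bleeding or signs or symptoms suggestive of bleeding with confirmatory imaging techniques which can detect the presence of blood". Major bleeding, including bleeding at the intracranial site, and CRNM bleeding must both meet that description. Together they form the primary safety endpoint (Protocol 8.3.4, SAP 4.4).

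**Hemorrhage analysis.** SAP 7.6.1 lists "The proportion of subjects with intracranial hemorrhage" beside the composite and all reported bleeding. Its opening sentence concerns adjudicated events, from first dose to 4 days after last dose. Neither document defines intracranial hemorrhage separately.

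**A central hemorrhage reading at baseline.** Item 5 of SAP Table 7.2.2-1 makes misdiagnosed intracranial hemorrhage a relevant deviation, "as determined by the central reader based on the baseline study specific MRI (presence of type 1 or 2 parenchymal hematoma". No Day 28 counterpart appears.

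**The concern.** One pair of scans supplies the silent part of the efficacy endpoint but, as written, supplies nothing systematic to safety. Subjects are within 48 hours of a stroke or TIA at randomization and receive an antiplatelet drug or placebo on top of ASA. Protocol 1.5 names bleeding as a potential risk of any antithrombotic and promises close monitoring for it.

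Two things are at stake. The first is the absolute rate: a new hematoma without symptoms may be on the Day 28 scan and appear in no bleeding table, and whether it appears depends on site practice. The second is the balance of benefit and harm by dose. If silent bleeding rose with dose, the trial would count the MRI benefit and could miss the MRI harm.

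**Working it through.** **Step 1. Set the two sides next to each other.**

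| | Silent infarct | Silent intracranial bleed |
|---|---|---|
| Scheduled scan | Baseline and Day 28, all subjects (Protocol 5.3.1) | Same scans |
| Central reading specified | Both scans compared (5.4.2, 7.2) | Baseline only, as a deviation criterion (SAP Table 7.2.2-1) |
| Route to an endpoint | IAC result enters the primary efficacy endpoint (SAP 4.1) | No route from IAC to CEC or to the sites is stated |
| Primary endpoint on that side | Counts | Cannot count: not clinically overt (5.3.2) |

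**Step 2. Follow one asymptomatic hematoma present on the Day 28 scan.**

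- Major bleeding: not met. The intracranial site criterion applies only to acute clinically overt bleeding.
- CRNM bleeding: not met, for the same reason. The primary safety endpoint is therefore not met.
- All bleeding, intracranial hemorrhage and adverse events: possible. A site may read the scan (5.3.1) and complete an (S)AE form for bleeding (5.3.2), or record significant worsening as an AE (6.7). Protocol 8.4.3 keeps investigator-reported endpoint events in the safety analyses whether or not adjudication confirms them. Every one of these routes starts with an optional local read.

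**Step 3. Denominators.** The plan has no silent-bleed figure to reproduce; only its sample size can be checked. Protocol Synopsis and 8.1: 1240 evaluable, about 5% without post-randomization data, 1312 randomized.

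- 1240 / 0.95 = 1305.3, rounded up to 1306, against 1312 stated. This agrees with an allowance of about 5%.
- Evaluable on placebo: 348 × 1240/1312 = 329. Evaluable on 8 mg: 270 × 1240/1312 = 255.

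The number with both scans readable could be lower than 1240.

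**Step 4. Absolute size, under an assumed rate of 1% to 4%.**

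- All evaluable: 1240 × 0.01 = 12.4; 1240 × 0.04 = 49.6. About 12 to 50 subjects.
- 8 mg arm: 255 × 0.01 = 2.6; 255 × 0.04 = 10.2. About 3 to 10 subjects.

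These are counts that the planned tables would not systematically contain. Local reports would recover an unknown share.

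**Step 5. Difference from placebo.** If silent bleeding is equally frequent, say 2% in both arms, the expected counts are 329 × 0.02 = 6.6 and 255 × 0.02 = 5.1. The rate difference is 0, so leaving these bleeds out understates nothing between arms. If the rates differ, the excess is compared below with the planned infarct reduction of 14% × 30% = 4.2 points. Power is for a two-sided 5% comparison of two proportions, Φ((d − 1.96·se₀)/se₁), with se₀ from the pooled rate and se₁ from the separate rates.

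| Assumed silent bleeds, placebo vs 8 mg | Expected cases | Excess (points) | 4.2 minus excess | Power |
|---|---|---|---|---|
| 0.5% vs 1% | 1.6 vs 2.6 | 0.5 | 3.7 | 11% |
| 1% vs 2% | 3.3 vs 5.1 | 1.0 | 3.2 | 18% |
| 2% vs 4% | 6.6 vs 10.2 | 2.0 | 2.2 | 31% |
| 2% vs 6% | 6.6 vs 15.3 | 4.0 | 0.2 | 70% |

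Worked line, 1% vs 2%: pooled rate (3.29 + 5.10)/584 = 0.0144; se₀ = 0.00993; se₁ = 0.01034; (0.010 − 1.96 × 0.00993)/0.01034 = −0.91; power 18%.

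The fourth column weighs one silent bleed as equal to one infarct, which is only a yardstick. The power column shows that a Day 28 row would serve estimation, not testing.

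**The case against.** A reader might infer that intracranial hemorrhage is captured only when overt and that silent bleeds never reach a safety endpoint. The documents do not support that. The overt requirement belongs to the major and CRNM definitions. Intracranial hemorrhage and all bleeding are separate endpoints without it, the referral rule sets a minimum, and the site routes in Step 2 exist. What remains is that these routes are unsystematic.

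A second inference is that differences from placebo are understated and the trial tilts toward the drug. That needs more silent bleeding on drug, and the documents give no evidence of it either way.

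A third is that every missed case would already have been scanned. The plan itself allows for about 5% without post-randomization data. Nor do the documents show that every hemorrhagic change would be visible: FLAIR and DWI are the only sequences named, and for infarction. The baseline criterion supports type 1 or 2 parenchymal hematoma and no more.

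It can also be said that the IAC and CEC charters and the imaging manual may already provide for a Day 28 hemorrhage read. Protocol 7.2 leaves the committee's full role to its charter, and the baseline hematoma read in the SAP shows that 7.2 is not a complete list. This stands: the finding concerns what the protocol and SAP specify.

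Finally, an adapted ISTH bleeding definition is a legitimate choice, and a scan finding fits badly into SAP 7.6.1. It has no onset date, subjects who stop early are still scanned at Day 28 and may be beyond the 4-day window, and Part 2 has no MRI after Day 28. These points argue for a separate row, and the fix follows them.

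**Conclusion.** The point holds as a gap in ascertainment, not as an error or contradiction. The protocol and SAP specify no systematic hemorrhage read of the Day 28 MRI and no route from the IAC to the bleeding endpoints. Asymptomatic intracranial hemorrhage cannot meet the primary safety endpoint as defined, and it enters other tables only through optional site reading and reporting.

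Absolute rates of intracranial bleeding are under-ascertained to the extent that such bleeds occur and sites do not report them. The size, about 12 to 50 of 1240, rests wholly on an assumed 1% to 4%. Any effect on the difference from placebo is conditional on silent bleeding being more frequent on drug. The change is worth making because the scans and blinded readers are already in place and the SAP already has a central reader classify hematoma at baseline.

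**What to change.** **Protocol 7.2 (and the IAC charter).** Have the same blinded readers record new type 1 or 2 parenchymal hematoma on the Day 28 MRI compared with the baseline MRI, using the classification in item 5 of SAP Table 7.2.2-1.

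**SAP 7.6.1.** Add a separate row, new parenchymal hematoma on Day 28 MRI, by arm, with 95% CIs and differences from placebo. The denominator is treated subjects with both scans readable. Count the finding irrespective of the last-dose-plus-4-days window. Limit any combined overt-or-MRI-detected figure to Day 28, so that 28-day imaging is not mixed with 90-day clinical capture in Part 2. Leave the overt bleeding endpoints as they are.

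**Cost.** One item on the central read form and one table row, with no added visit or scan. The central read takes slightly longer, and the hemorrhage figure will look less favourable. Two limits remain. Silent bleeds from Day 28 to Day 90 in Part 2 stay unseen. The baseline MRI may be taken up to 24 hours after randomization, possibly after the first dose, so a bleed before that scan would not count as new. If the IAC charter already requires the Day 28 read, cite it and add only the SAP row.

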8 STATISTICAL CONSIDERATIONS

8.1 Sample Size Determination

The primary efficacy endpoint of the study is the incidence of a composite of symptomatic ischemic stroke by Day 28 and unrecognized brain infarction at Day 28. Sample size calculations were performed for detecting a dose-response effect with the MCP-MOD methodology using simulations with the DoseFinding package in R¹⁴. Simulations of 1000 clinical trials were performed, assuming a true incidence for placebo of 14%, a maximum relative risk reduction of 30% for BMS-986141 8 mg relative to placebo, and relative reductions of 75% and 90% of the maximum for the 0.8 and 4.8 mg doses, respectively. Candidate models included an Emax model and a logistic model.

Initially, randomization will be limited to the two lower doses of BMS-986141 (0.8 mg or 4.8 mg) or placebo in a 1:1:1 ratio until after DMC review of safety and laboratory data from the Day 28 study visit for at least 10% of planned total subjects (approximately 132 subjects). If the DMC recommends proceeding to inclusion of the highest dose (8 mg), subsequent randomization will be in a 1:1:1:1 ratio. Based on the staggered randomization as shown in Table 8.1-1 and the assumptions above, the study will have at least 80% power to demonstrate a dose-response relationship, using a 1-sided type I error rate of 15%. A total sample size of 1312 randomized subjects accounts for about 5% of subjects without post-randomization data.

Table 8.1-1: Randomization Targets^a

	Placebo	0.8 mg	4.8 mg	8 mg
Prior to interim safety review by DMC: 132 subjects (1:1:1 randomization ratio)	44	44	44	0
Additional subjects randomized while interim safety tables are being generated and reviewed by the DMC (not included in DMC safety interim analysis): 100 subjects (1:1:1 randomization ratio)	34	33	33	0
After interim safety review by DMC: 1081 subjects	270	270	270	270
Total: 1312 subjects	348	347	347	270

^a Numbers shown for each treatment group are estimates based on randomization ratio. Actual numbers could be slightly different based on randomization block size.

8.2 Populations for Analyses

- The Enrolled Subjects Data Set will consist of all subjects who sign informed consent.
- The Randomized Subjects Data Set will consist of all randomized subjects regardless of whether they received treatment. This is also known as the Intent to Treat (ITT) population. This will be the primary efficacy data set. Data in this data set will be analyzed based on randomized treatment group.
- The Treated Subjects Data Set will consist of all subjects who receive at least one dose of study medication during the treatment period. This will be the primary safety data set. Data in this data set will be analyzed based on randomized treatment, except in the following cases:
 - If a subject received the same incorrect treatment throughout the study (until either Day 28 or Day 90, or until discontinuation of the study drug), then the subject will be analyzed based on the treatment received.
 - If a subject received study drug from more than one treatment group, and none of the administrations were consistent with the assigned randomized treatment group, then the subject will be analyzed based on the first treatment received.

- The Pharmacodynamic analysis dataset will consist of subjects in the Randomized Subject Dataset who have at least one pharmacodynamic endpoint assessed.
- The Pharmacokinetic analysis dataset will consist of all subjects who receive BMS-986141 and have at least one post dose PK sample. Additionally, the evaluable PK population is defined as subjects who have adequate PK profiles on Day 1.

8.3 Endpoints

8.3.1 Primary Endpoint(s)

The primary efficacy endpoint of the study is the incidence of a composite of symptomatic ischemic stroke by Day 28 and unrecognized brain infarction assessed by MRI at Day 28.

8.3.2 Secondary Endpoint(s)

Secondary endpoints include:

- The incidence of major adverse cardiovascular events (MACE) by Day 90, defined as a composite of adjudicated recurrent stroke, myocardial infarction, or CV death
- The incidence of a composite of adjudicated recurrent ischemic stroke, myocardial infarction, or CV death
- The incidence of adjudicated symptomatic recurrent stroke (including fatal and non-fatal) by Day 28
- The incidence of the composite of unrecognized brain infarction assessed by MRI at Day 28 and MACE by Day 90

8.3.3 Exploratory Endpoint(s)

[REDACTED]

[REDACTED]

[REDACTED]

[REDACTED]

[REDACTED]

[REDACTED]

[REDACTED]

8.3.4 Safety Endpoints

The primary safety endpoint is incidence of a composite of adjudicated major bleeding and adjudicated clinically relevant non-major (CRNM) bleeding during the treatment period.

Additional safety endpoints include the incidence of adjudicated major bleeding events, all bleeding events, intracranial hemorrhage events, as well as the incidence of AEs and markedly abnormal standard clinical laboratory test results.

